- Oswestry Pain and Disability (ODI) assessment at baseline (Day 1), Day 4, and Day 14

The ODI questionnaire contains 10 questions with one answer each for pain intensity, personal care, lifting, walking, sitting, standing, sleeping, sex life [if applicable], social life, and traveling). Scores are assigned for each section from 0 to 5 (5 being the worst case).

ODI scores are derived based on the methods described in [Mehra et.al. \(2008\)](#). The method is equivalent to an ODI score calculated as $(\text{total score} \times 2) / (\text{number of sections answered} / 10)$, rounded to the nearest integer. The total score is the sum of the individual section scores.

- Use of study-provided rescue medication [acetaminophen tablets (500 mg)] measured daily and assessed as number of rescue tablets administered by the subject and recorded via smartphone/use of trial application.
- Quality of sleep as rated by subjects daily from Day 1 to Day 14. The rating scale is 1-5, where 1 = not at all to 5 = slept all night. Assessments are collected via smartphone/use of trial application.
- Visual Analogue Scale (VAS) for subject-reported sleepiness as measured in the clinic on at Day 4 via tablet ePRO. Scale is from 0 to 10, where 0 = alert, wide awake to 10 = very sleepy, difficulty remaining awake.

6.4.2 *Description of Safety Variables*

Safety variables include:

- Adverse events and serious adverse events

- Clinical evaluations including vital signs (blood pressure, heart rate, respiratory rate, body temperature), orthostatic effects on blood pressure, physical examinations, and 12-lead electrocardiogram (ECG)
- Laboratory tests including blood chemistry, hematology, and urinalysis

6.4.2.1 *Adverse Events*

An AE is defined as any untoward medical occurrence in a subject administered a medicinal product and which does not necessarily have to have a causal relationship with this treatment. An AE can therefore be any unfavorable and unintended sign (for example, an abnormal laboratory finding), symptom, or disease temporally associated with the use of a medicinal product, whether or not considered related to this medicinal product. AEs occurring after the initiation of the study drug treatment are referred to as treatment-emergent adverse events (TEAEs).

See Section 15.1 of the study Protocol for further details regarding the definition of AEs.

6.4.2.2 *Serious Adverse Events*

An SAE or reaction is any untoward medical occurrence that at any dose:

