SRMH values will be summarized categorically by treatment group for Days 4 and 14 for the ITT Population. The frequency and percentage of subjects in each response category will be presented. The comparison of each group to placebo will be conducted using a Wilcoxon Rank Sum test for the Day 14 values and p-values presented.

7.4.5.5 *Fingers to Floor Distance*

Fingers to floor distance will be assessed at Baseline, Day 4, and Day 14 and will be analyzed using a linear test of trend similar to the primary endpoint on Day 14. Pairwise estimates of the observed value will be presented.

7.4.5.6 *Global Symptom assessments (CGI and PGI)*

Global symptom assessments will be summarized by treatment group for the ITT population. CGI-S and PGI-S will be assessed at the baseline visit only. CGI-C and PGI-C will be assessed at Day 4 and Day 14. The frequency and percentage of subjects in each response category at Baseline, Day 4 and Day 14 will be presented. The comparison of each group to placebo will be conducted using a Wilcoxon Rank Sum test for the Day 14 values and p-values presented.

7.4.5.7 *Quality of Sleep*

Quality of sleep will be analyzed using the same methods described for the global symptom assessments in section 7.4.5.6. The comparison of each group to placebo will be conducted using a Wilcoxon Rank Sum test for the Day 14 observed values.

7.4.5.8 *Time to Pain Relief*

Time to pain relief (days) will be assessed using the NRS assessment of subject rating of pain over the past 12 hours. NRS assessments on or after Day 2 will be considered for time to relief. The first post-baseline occurrence of an AM or PM 12-hour NRS score equal to 2 or lower (0 = no pain, 10 = worst possible pain) will be used as the criterion for relief.

Subjects who withdraw from the study prior to the end of treatment visit or who complete the treatment period without having met the criteria for relief will be censored at the time of their last NRS assessment. Time to relief will be presented in days as (date of relief/censoring – date of first dose + 1).

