Observed ODI score and change from baseline will be summarized descriptively for each treatment group for the ITT population. Each dose group will be compared to placebo using an ANCOVA model with observed value as the response, main effects for treatment group and a covariate adjusted for the baseline ODI score. The LSM, LSMD, 95% CI and p-values will be presented at Day 14.

Individual section scores will be summarized separately for the ITT population by treatment group. The frequency and percentage of subjects in each response category at Baseline, Day 4 and Day 14 will be presented. The comparison of each group to placebo will be conducted using a Wilcoxon Rank Sum test for the Day 14 values and p-values presented.

7.4.5.11 *Visual Analogue Scale of Sleepiness*

The Day 4 VAS ratings of sleepiness will be summarized descriptively by treatment group for the ITT population. Each dose group will be compared to placebo using an ANOVA model with the observed values as the response and main effects for treatment group. The LSM, LSMD, 95% CI and p-values will be presented.

7.4.5.12 *Daily Activities*

Daily activity scores will be summarized categorically for Days 1 to 14 by treatment group for the ITT population. The frequency and percentage of subjects in each response category will be presented. The comparison of each group to placebo will be conducted using a Wilcoxon Rank Sum test for the Day 14 values and p-values presented.

7.4.6 *Statistical/Analytical Issues*

7.4.6.1 *Adjustments for Covariates*

The MMRM model to test for linear trend for the primary endpoint will include a covariate adjustment for the baseline value. Secondary endpoints utilizing an MMRM will be analyzed similarly when a baseline value is captured.

7.4.6.2 *Handling of Dropouts or Missing Data*

Primary and secondary endpoints including all NRS assessments (right now, past 12 hours, past 1 hour, at rest, on movement), Fingers to floor Distance, Clinician's Global Impression, and Oswestry Disability Index assessments will be analyzed using both observed data and data imputed using last observation carried forward (LOCF), if the dropout rate is $\geq 5\%$ (20/400 subjects). In the LOCF method, the most recent non-missing value for the endpoint is carried forward to replace a missing value at a post-baseline visit within a subject. Baseline values will not be carried forward.

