Methods for multiple imputation (MI) for missing data may be explored for endpoints if the dropout rate is $\geq 15\%$ (60/400 subjects).

7.4.6.3 *Interim Analyses and Data Monitoring*

There are no interim analyses planned, nor is there a plan to establish a data monitoring committee for this study.

7.4.6.4 *Multicenter Studies*

This is a multicenter study, with approximately 45 sites expected to participate. Efficacy data collected from all study sites will be pooled for data analysis. The effect of study site on the efficacy analysis results may be explored post-hoc, as needed.

7.4.6.5 *Multiple Comparisons/Multiplicity*

There will be no adjustments for multiple comparisons in the efficacy analysis for this study. All of the above analyses will be conducted using two-sided tests at the $\alpha = 0.05$ level of significance.

7.4.6.6 *Use of an “Efficacy Subset” of Subjects*

The primary efficacy analysis will be performed on the ITT population; the PP population will be utilized as a sensitivity analysis for the primary endpoint and secondary endpoints, including NRS (right now, past 12 hours, past 1 hour, at rest, on movement), Subject Rating of Medication Helpfulness, Fingers to Floor Distance, Clinician’s Global Impression assessments, and Oswestry Disability Index. The PP population will exclude subjects with major protocol violations.

7.4.6.7 *Active-Control Studies Intended to Show Equivalence*

This study does not include an active-control product and is not intended to demonstrate equivalence between any two drug products.

7.4.6.8 *Examination of Subgroups*

There are no planned analyses to assess efficacy results by subgroups.

7.4.7 *Plasma Concentrations*

Plasma concentration measurements will be summarized in a separate report and is outside the scope of this SAP.

7.4.8 *Pharmacokinetic Analysis*

Pharmacokinetic analysis will be summarized in a separate report and is outside the scope of this SAP.

7.5 **Safety Evaluation**

Safety analysis will be carried out for the Safety Population, which will include all subjects who receive at least one dose of study drug. Subjects who do not complete the study, for whatever reason, will have all available data up until the time of termination included in the analysis. For safety analysis presented by study visit, the baseline value will be defined as the last value reported prior to first study drug administration. All analyses will be presented by treatment group.

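### The ODI comparison is a Day 14 ANCOVA that leaves out the Day 4 score; a repeated-measures model would use it at very little cost

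*SAP*

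**What the plan says.** SAP 6.4.1.2 lists the endpoint as "Oswestry Pain and Disability (ODI) assessment at baseline (Day 1), Day 4, and Day 14". SAP 7.4.5.10 sets the comparison: "Each dose group will be compared to placebo using an ANCOVA model with observed value as the response", with treatment as the main effect and baseline ODI as covariate. Of the timing it says: "The LSM, LSMD, 95% CI and p-values will be presented at Day 14". There is no visit factor. Day 4 ODI is summarised descriptively but not modelled.

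SAP 7.4.6.2 sets the missing-data rule. ODI is one of the named endpoints: "Oswestry Disability Index assessments will be analyzed using both observed data and data imputed using last observation carried forward (LOCF", provided overall dropout is at least 5% (20/400). Under LOCF, "the most recent non-missing value for the endpoint is carried forward to replace a missing value at a post-baseline visit", and baseline is never carried. Beyond that, "Methods for multiple imputation (MI) for missing data may be explored for endpoints if the dropout rate is" at least 15% (60/400). Protocol 17.4.2.3 plans LOCF plus an observed-data run without a threshold. Protocol 17.4.2.2 assigns baseline-adjusted ANCOVA to all secondary endpoints that it does not treat separately, and ODI falls there.

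Two other continuous scores are taken at the same three clinic visits. NRS 'right now' has the MMRM of SAP 7.4.4 and 7.4.5.1. Finger-to-floor distance (FFD), in SAP 7.4.5.5, "will be analyzed using a linear test of trend similar to the primary endpoint on Day 14".

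Protocol 11.2.4 has ODI repeated at an early-termination visit. SAP 7.1.2 reserves the label Day 14 for the scheduled visit, and 7.4.5.10 does not say whether early-termination ODI enters the model.

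**The concern.** ODI is the trial's disability questionnaire. A subject with baseline and Day 4 ODI who leaves before Day 14 carries information about the Day 14 result, because the two scores are correlated. A single-visit ANCOVA on observed data discards it. If subjects who do badly at Day 4 leave one arm more than another, the completers are no longer comparable. Adjusting for baseline does not repair that, since the selection happened after baseline.

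LOCF brings the Day 4 score back, but treats it as a Day 14 score in an acute condition where pain and disability are expected to change between the two visits. The plan would then hold two ODI results that may err in opposite directions, and the SAP does not say which governs. A likelihood-based repeated-measures model uses the Day 4 score without that assumption, and the SAP already relies on such a model for NRS 'right now' and FFD.

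**Working it through.** **The plan's own figure.** The documents give no power or sample size for ODI. Their NRS figure reproduces: 80 per group, difference 0.9, SD 2.0, two-sided 5%. The noncentrality is 0.45 × √(80/2) = 2.846. The normal approximation gives Φ(2.846 − 1.960) = 81.2% and the t distribution 80.8%, against the stated minimum of 80% and 81% in Protocol Table 1. Nothing below changes that figure.

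**Where the bias comes from.** Let b be the slope of Day 14 ODI on Day 4 ODI in completers, adjusted for arm and baseline. Let g be the baseline-adjusted arm difference in Day 4 ODI, in all subjects or in completers. By the omitted-variable identity,

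completers' ANCOVA − MMRM = b × (g in completers − g in all).

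So bias needs dropout to shift the Day 4 arm difference. If both arms lose subjects by the same Day 4 rule and treatment has no Day 4 effect, the shift is zero.

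**Assumed inputs (none is in the documents).** Correlations: baseline–Day 4 0.5, baseline–Day 14 0.4, Day 4–Day 14 0.5 or 0.7. Then b = (0.5 − 0.5 × 0.4)/(1 − 0.5²) = 0.40, or (0.7 − 0.2)/0.75 = 0.67. Dropout is logistic in Day 4 ODI. One dose is compared with placebo in large simulated samples. The true Day 14 effect is 0.4 SD, or 0 in the no-effect case.

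| Dropout setting | Bias of completers' ANCOVA (SD) |
|---|---|
| Same rule in both arms, no Day 4 effect, 10–15% | 0.00 |
| Same rule, Day 4 effect 0.2–0.4 SD, 10–15% in placebo | 0.004 to 0.038 |
| Placebo 15% leaving on bad Day 4 scores, active 10% at random | 0.040 to 0.067 |
| Opposite rules (placebo worse leave, active better leave), 5% per arm | 0.028 to 0.048 |
| Opposite rules, 15% per arm | 0.082 to 0.136 |

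The non-zero biases are all toward no effect. MMRM bias was within 0.002 SD throughout; every setting is missing at random given Day 4. The last row agrees with the identity: 0.082/0.40 and 0.136/0.67 both imply a shift of about 0.20 SD in the Day 4 difference. The rows with arm-different rules use one log-odds per SD of Day 4 ODI. A steeper slope gives more, so 0.136 is the largest value in these settings and not a bound.

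**Scale.** With 80 per arm, the standard error of the adjusted difference is about √(2/80) × √(1 − 0.4²) = 0.145 SD. The extreme case is therefore 0.136/0.145 = 0.94 standard errors. The largest same-rule case is 0.038/0.145 = 0.26. If the ODI SD were 17 points, these would be 0.136 × 17 = 2.3 and 0.038 × 17 = 0.6 points.

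**LOCF.** Add an assumed 1 SD common improvement from Day 4 to Day 14, a Day 4 effect of 0.2 SD and a true Day 14 effect of 0.35 SD. With placebo 15% leaving on bad scores and active 10% at random, ANCOVA gives 0.28–0.31, LOCF 0.42–0.44 and MMRM 0.35. The direction of the LOCF error is not fixed. With 15% random dropout in both arms and no common improvement, a true effect of 0.40 came out as 0.37.

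**Information.** With random dropout d in each arm, the ANCOVA variance relative to the MMRM is 1/(1 − r²d), where r is the Day 4–Day 14 correlation given baseline. Here r² = 0.3²/(0.75 × 0.84) = 0.143 or 0.5²/0.63 = 0.397. At d = 0.10 the ratio is 1.01 to 1.04, and at d = 0.15 it is 1.02 to 1.06. At 15%, 68 completers per arm are worth 68 × 1.02 = 69 to 68 × 1.06 = 72 under the MMRM. Borrowing the NRS effect of 0.45, completers-only power falls from 80.8% to 78.7%, 76.5% and 74.1% at 5%, 10% and 15% dropout. The MMRM recovers only part of that loss.

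**The case against.** The ANCOVA is pre-specified, and the SAP follows the protocol here, so it is neither a departure nor an error. ODI is one of many secondary endpoints in a Phase 2 dose-ranging trial without multiplicity adjustment (SAP 7.4.6.5). The larger biases need arm-specific dropout rules that nobody has observed. In some of those settings LOCF roughly offsets the ANCOVA's attenuation. The MMRM is unbiased here because each setting satisfies its missing-at-random assumption. All of this stands and limits the importance of the point. It does not remove the gain: with complete data the two models give essentially the same Day 14 contrast, and with missing data the MMRM uses scores that the trial already holds.

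Three stronger readings are tempting and not supported:

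- A reader might infer that dropouts contribute nothing to the ODI comparison. That is true of the observed-data run, and of the whole comparison only below 5% dropout. From 5%, SAP 7.4.6.2 requires an ODI analysis that carries the last post-baseline value.
- A reader might infer that the estimate is biased whenever leaving depends on Day 4 ODI. The first row of the table shows otherwise.
- A reader might infer that every other Day 4/Day 14 score has an MMRM. Medication helpfulness (SRMH), CGI-C and PGI-C are tested by Wilcoxon on Day 14 values (SAP 7.4.5.4 and 7.4.5.6).

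The missing linear trend for ODI is a separate matter. At effect size 0.4, Protocol Table 1 gives trend 81–92% power in the graded or stepped patterns against 71% pairwise, but only 62% if all doses are equal. Those are NRS planning figures, so they do not settle the choice for ODI.

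**Conclusion.** The point holds as an inexpensive improvement to a secondary analysis. The observed-data ODI comparison ignores Day 4 and drops subjects without Day 14. LOCF uses the Day 4 score, but under an assumption that is hard to defend in an acute condition. The observed-data estimate can be biased by 0 to about 0.14 SD against a true 0.4 SD in the settings examined. The top of that range comes from opposite dropout rules in the two arms; a shared rule gave at most 0.04 SD. The sizes rest on assumed correlations, dropout rates and mechanisms, and the MMRM's advantage rests on dropout being explained by baseline and Day 4 ODI. Neither the primary analysis nor the sample size is affected.

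**What to change.** In SAP 7.4.5.10, make the main ODI comparison an MMRM with Day 4 and Day 14 ODI as responses; treatment, visit and treatment-by-visit as fixed effects; and baseline ODI as covariate. Baseline should not also be a response. The primary model in SAP 7.4.4 lists Day 1/Baseline as a visit level as well as a covariate, so that code cannot be copied unchanged. Report the Day 14 LSMDs against placebo with 95% CIs. Keep the ANCOVA, observed and LOCF, as supportive, and state whether early-termination ODI is used. List the change in SAP 7.7.1 before unblinding. A linear trend for ODI is optional.

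Cost: a few lines of SAP text and minor reprogramming. No new data are needed.

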7.5.3 Deaths, Other Serious Adverse Events, and Other Significant Adverse Events

All deaths during the study, including the post treatment follow-up period, will be listed by subject, to include the primary cause of death. Serious AEs and other significant AEs, including those that led to discontinuation, interruption or dose reduction of the study drug, will be provided in separate subject data listings.

7.5.4 Clinical Laboratory Evaluation

7.5.4.1 Hematology and Chemistry

All descriptive summaries of laboratory results will be based on data analyzed by the central laboratory and presented in Système International (SI) units, as suggested by the Center for Biologics Evaluation and Research and the Center for Drug Evaluation and Research *Position on Use of SI Units for Lab Tests* (Oct 2013). All data will be included in by-subject data listings. Laboratory measurements identified as abnormal (i.e., outside the normal range) will also be listed separately by subject, laboratory test, and unit.

Serum chemistry and hematology clinical laboratory measurements will be summarized by treatment group and for total tolperisone treated subjects at Baseline, Day 14, and at Day 14/ET. Descriptive statistics will be presented for observed values and changes from baseline at each visit.

7.5.4.2 Urinalysis

Urinalysis and microscopic urinalysis results will be summarized in by-subject data listings.

7.5.4.3 Pregnancy Test

Pregnancy test results will be presented in a by-subject data listing

7.5.4.4 *Alcohol Breathalyzer Test*

Alcohol breathalyzer test results will be presented in a by-subject data listing

7.5.4.5 *Urine Drug Screen*

Urine drug screen results will be presented in a by-subject data listing

7.5.5 *Vital Signs, Physical Findings, and Other Observations Related to Safety*

7.5.5.1 *Vital Signs*

Vital sign parameters including blood pressure (standing, supine, orthostatic), heart rate, respiratory rate and body temperature will be summarized by treatment group and for total tolperisone treated subjects. Descriptive statistics will be presented for results and change from baseline at each visit where parameters were scheduled to be collected.

Orthostatic blood pressure will be calculated as the standing minus supine measurement for both systolic and diastolic blood pressure.

Weight will be converted from lbs to kg using a conversion factor of 0.4536.

7.5.5.2 *12-Lead Electrocardiogram*

Twelve-Lead ECG interval parameters will be summarized categorically as normal, clinically significant abnormal, and not clinically significant abnormal by treatment group and for total tolperisone treated subjects at each scheduled visit.

7.5.5.3 *Neurological Examination*

Results of the neurological examination will be summarized categorically as improved, stable, and deteriorated by treatment group and for total tolperisone treated subjects at each scheduled visit.

7.5.5.4 *Physical Examination*

Results of the physical examination will be presented in subject data listings by subject and study visit.

7.5.5.5 *Concomitant and After-Treatment Medications*

Medications will be coded using the World Health Organization Drug Dictionary Enhanced (WHODDE), version B3 March 1, 2018. Medications entered on the eCRF will be mapped to Anatomic Therapeutic Chemical (ATC) drug class (level 4) and drug name.

Concomitant and after-treatment medications will be summarized separately for the Safety Population. The study phase of each medication will be determined programmatically based on medication start and end dates. A prior medication is defined as any medication administered prior to the date of the first dose of study drug. A concomitant medications is defined as any

medication administered on or after the date of the first dose of study drug through 24 hours after the date of last dose of study drug. If medication time is not available, any medication administered on or after the date of first dose through the day after the date of last dose (+1 day) will be considered concomitant. An after-treatment medication is defined as any medication administered greater than 24 hours (or >1 day) after the date of the last dose of study drug through the date of the follow-up visit (Visit 4/Day 28).

A medication may be defined as both prior and concomitant. If it cannot be determined whether a medication was received prior to the start of study drug dosing due to partial or missing medication start and/or end dates, it will be considered a prior medication. Likewise, if it cannot be determined whether a medication was received after the start of study drug dosing, it will be considered concomitant.

For both concomitant, and after-treatment medications summaries, the number and percentage of subjects receiving any medication will be summarized by treatment group and for total tolperisone treated subjects, as will the number and percentage receiving any medication by ATC drug class and generic drug name.

Subjects reporting use of more than one medication at each level of summarization (any medication received, ATC class, and generic drug name) will be counted only once. ATC class terms will be displayed by descending order of incidence, as will generic drug names within each ATC class. The study phase during which each medication was received (e.g., prior, concomitant, or both) will be presented on the listing of prior and concomitant medications.

A summary of concomitant analgesic medications received, outside of the study-provided medication, will also be presented. These medications will be identified from list of generic drug names and indications as determined by the sponsor prior to data base closure. Analgesic medications taken on Day 1 will not be considered as concomitant as use was allowed per protocol on Day 1 of treatment.

All medications will be presented in a data listing by subject and medication name. The study phase during which each medication was received (e.g., prior, concomitant, or after-treatment) and whether the medication is a rescue medication will be presented on the listing.

